4.10.3 Follow-up visits (2, 6, and 12 weeks postpartum)

• Each participant will have follow-up visits at home or healthcare facility whichever is preferred except the 6 weeks visit which as routine should be at the health care facility.

The following steps will be taken at the follow up visits:

- 1. Go to REDCap, using the participant's study ID-
 - Complete and submit the Edinburgh Postnatal Depression Scale (EPDS) e-form (Appendix xi) at 6 weeks visit.
 - Complete and submit the Maternal infant bonding scale e-form (Appendix xii) at 6 weeks visit.
 - Complete and submit the fatigue scale e-form (Appendix xiii) at 6-week visit.
 - Complete and submit the quality of life (WHOQOL BREF) scale e-forms (Appendix xiv) at 6 weeks visit.
 - Evaluate for the presence of any symptom and sign (adverse event(s) AEs)) and if any,
 complete and submit the adverse event e-form for all follow up visit.

The visit e-CRF will be available to you ONLY after completing and submitting the above steps on REDCap.

- Evaluate compliance to study drug and document in the e-CRF.
- Complete follow-up visits e-CRF (Appendix xv) and relevant source documents
- Re- supply study drug (control arm) in an amount sufficient to last until the next follow up visit up to the 6th week visit.
- Counsel and necessary referral (e.g., family planning clinic, psychosocial support etc.).

2. Additional steps

- Perform malaria rapid diagnostic test (RDT) with SD BIOLINE Malaria Ag P.f and complete the *Malaria POCT worksheet* as appropriate (2- and 6-week postpartum visits).
- Do hemoglobin concentration check with the haemoglobinometer at every follow up visit. And complete Hb check worksheet as appropriate.
- Take blood samples for laboratory tests as indicated for visit type and complete the blood sample collection log on REDCap. This sample can also be used for the hemoglobin concentration check.
- Counsel as appropriate based on any queries they might have about their health or that of their newborn/baby.

The research team at site will be responsible for the visits and attending to the participant and resupplying the participants with the study drugs at two weeks.

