4.5 Blinding

This study is a multicenter parallel, open label, superiority randomized controlled trial. It is impossible to blind the treatment allocation as the intervention is administered intravenously, and the control is administered orally. However, the primary outcome data will be objectively determined by laboratory evaluation and will be collected without bias. For the subjective secondary outcomes, using the Edinburgh Postpartum Depression Scale (EPDS), Quality of Life questionnaire, fatigue scale, Maternal Infant Bonding questionnaire and an adverse event form, the research nurse performing data collection for these outcomes will be blinded to group allocation. These patients' reported outcomes measures will be completed without knowledge of the group allocation except for data on treatment compliance. Data on treatment compliance will be collected only after all other outcome data for the individual's visit has been completed and submitted.

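### Section 4.5 says compliance is collected after all other outcome data, but the visit steps in 4.10.3 place it before the visit e-CRF, the hemoglobin reading and the blood samples

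*Protocol*

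**What the plan says.** Section 4.5 (Blinding) explains how an open-label trial will limit assessment bias, and it makes three separate statements.

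- **Primary outcome:** it relies on objectivity. The text says that "the primary outcome data will be objectively determined by laboratory evaluation and will be collected without bias".
- **Subjective outcomes** (depression, quality of life, fatigue, bonding, adverse event form): it promises that "the research nurse performing data collection for these outcomes will be blinded to group allocation".
- **Order of collection:** "Data on treatment compliance will be collected only after all other outcome data for the individual's visit has been completed and submitted".

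Section 4.10.3 gives the working sequence for the 2-, 6- and 12-week visits. Under step 1, staff submit the four scales (at six weeks) and the adverse event form (at every visit). The visit e-CRF becomes available only "after completing and submitting the above steps on REDCap". The next items, in order, are "Evaluate compliance to study drug and document in the e-CRF", then "Complete follow-up visits e-CRF (Appendix xv) and relevant source documents", then control-arm resupply, then counselling. Step 2, headed as additional steps, holds the malaria test, the instruction "Do hemoglobin concentration check with the haemoglobinometer at every follow up visit", and the blood samples.

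Section 3.1.1 defines the primary outcome as hemoglobin of at least 11.0 g/dl at six weeks. Section 4.9 lists two hemoglobin sources at that visit: the HemoCue reading on site and a full blood count analyzed at an external laboratory. Section 4.6.1 has women in the oral arm bring their empty sachets to each study visit for a pill count.

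**The concern.** Assessing compliance reveals the arm. One group has sachets and a pill count, and the other had a single infusion at enrollment. That is the evident reason for collecting compliance last. In the written procedure, however, compliance comes ahead of the hemoglobin check on which the primary endpoint may rest, and ahead of completion of the visit form.

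Several secondary outcomes in section 3.1.2 depend on history or judgement, such as breastfeeding or a new antibiotic prescription for presumed infection. Apart from the adverse event form, no form that precedes compliance is named for them. Any that sit in the visit e-CRF would be recorded just after the step that shows the arm.

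What is at stake is whether the protocol, and later the report, can claim a bias control that sites were not told to carry out.

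**Working it through.** **Order promised and order listed**

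| Item at the visit | Position required by 4.5 as worded | Position in 4.10.3 |
|---|---|---|
| Four scales, adverse event form | before compliance | before compliance (inside the gate) |
| Outcome items in the visit e-CRF, if any | before compliance | after compliance |
| Haemoglobinometer reading | before compliance | after compliance (step 2) |
| Blood samples | before compliance | after compliance (step 2) |
| Control-arm resupply | not addressed | after the visit e-CRF |

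The first row agrees. The next three do not. Six-week hemoglobin is outcome data by section 3.1.1, so the conflict reaches the primary-endpoint visit. The six-month visit in section 4.10.5 has no compliance step and is not affected.

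**Illustrative size, if the on-site reading defines the endpoint**

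The protocol gives no standard deviation for hemoglobin and no rate of altered readings, so both are assumptions here.

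- From section 4.3: 39% anemic on oral iron and 30% on IV iron. The planned difference is 39 − 30 = 9 points, and the average is (39 + 30)/2 = 34.5%.
- Assumed: six-week hemoglobin is normal with SD 1.2 g/dl and 34.5% of women below 11.0. Since Φ(−0.40) ≈ 0.345, the mean is 11.0 + 0.40 × 1.2 ≈ 11.48 g/dl.
- Women who could be moved up across the cut-off by 0.2 g/dl or less: P(10.8 < Hb < 11.0) = Φ(−0.40) − Φ((10.8 − 11.48)/1.2) = Φ(−0.40) − Φ(−0.57) ≈ 0.345 − 0.286 = 0.059.
- If 10% of these readings were moved in one arm only: 0.10 × 5.9 ≈ 0.6 percentage points.

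Only one side of the cut-off counts, because a shift in one direction cannot reclassify women who are already on the favorable side.

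**Range**

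| Assumed SD (g/dl) | Share between 10.8 and 11.0 | Shift if 5% are moved | Shift if 10% are moved | Shift if 20% are moved |
|---|---|---|---|---|
| 1.0 | 7.0% | 0.4 points | 0.7 points | 1.4 points |
| 1.2 | 5.9% | 0.3 points | 0.6 points | 1.2 points |
| 1.5 | 4.8% | 0.2 points | 0.5 points | 1.0 points |

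If the laboratory blood count defines the endpoint, the order of steps at the site has essentially no bearing on it.

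**The case against.** The strongest reply is that the sentence in 4.5 should be read in context. It follows directly on the statement that the patient-reported measures are completed without knowledge of the arm. On that reading, the other outcome data are the four scales and the adverse event form, which are exactly the forms the REDCap gate places before compliance, and the two sections agree. This is plausible and may be what was meant. But the sentence refers to all other outcome data for the visit, without limit. If the narrow meaning was intended, the wording claims more than the procedure provides.

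A second reply is that the heading of step 2 need not mean later in time. The list is numbered 1 then 2, though, and within step 1 compliance precedes the visit form in any case.

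A reader might also draw stronger conclusions, which the protocol does not support:

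- **That the order of steps is what unblinds the hemoglobin reading.** The trial is open label, site research nurses randomize (section 4.4), and 4.5 promises no assessor blinding for the primary outcome. Reordering lowers the chance of arm-aware recording but cannot guarantee concealment.
- **That resupply also comes before the outcome records.** It is listed after the visit e-CRF. The text ties it to two weeks and to the period up to the six-week visit, so it does not clearly precede the six-week reading, although Table 3 marks the control drug at that visit.
- **That the clinical outcomes can only be in the visit e-CRF.** Appendix xv is not shown. Infection or hemorrhage may well be captured on the adverse event form, which is submitted first. Breastfeeding is the clearest candidate for the visit form, and that is an inference.
- **That no protection remains.** The blinded nurse for the subjective outcomes and the gate on those forms are both intact.
- **That about 12% of women near the cut-off are at risk.** That figure counts both sides of 11.0 g/dl and doubles the effect of a shift in one direction.

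**Conclusion.** The point holds as a mismatch between a stated safeguard and the procedure meant to carry it out. As worded, 4.5 is not implemented in 4.10.3 for the on-site hemoglobin reading, the blood samples, or any outcome items in the visit e-CRF.

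The likely consequence is small. The illustrative shift of about 0.6 points rests on a normal distribution, an SD of 1.2 g/dl, an on-site endpoint and a 10% rate of moved readings. Nothing in the protocol suggests that readings would be moved at that rate. The protocol does not say whether the HemoCue or the laboratory value defines the primary outcome, and a laboratory definition would largely remove the concern for that endpoint. It would leave the history-based items, whose exposure cannot be sized without the form. The change is worth making because it is cheap, not because a material bias has been shown.

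**What to change.** Rewrite the list in 4.10.3 in this order:

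1. The scales and the adverse event form.
2. The hemoglobin check and the blood samples.
3. The outcome items of the visit e-CRF, completed and submitted.
4. A separate final form for compliance and pill count, which opens only after the preceding items are submitted, with resupply after it where it applies.

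The REDCap gating already in use can enforce this. The cost is one rewritten list and one more form gate, with no added visits or staff.

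If the narrower meaning was intended, limit the sentence in 4.5 to the subjective scales and the adverse event form, so that it does not claim protection for hemoglobin or the visit-form outcomes. That costs one sentence, but it gives up the modest protection that reordering would bring.

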4.10.4 Interim contacts and unscheduled visits

- The participant or the site clinician may request an interim contact or an unscheduled visit at any time during the study.
- Interim or unscheduled visits are usually adverse event (AE)-related visits in which health-related events, adverse drug effects, or abnormalities are reported.
- Other reasons for an interim or unscheduled visit not in response to an AE may include:
 - o To get more trial drugs in cases of loss or misplacement.
 - o To ask questions and discuss problems with study compliance
 - o Interim examination examination requested but no complaints or symptoms
- All interim contacts and unscheduled visits will be documented in the participants study records and visit e-CRFs.

4.10.5 End of study (EOS at six months post-partum)- visit

• All participants will complete the study at six months postpartum and all relevant data will be captured into all the appropriate study visit e-CRF.

These steps will be taken at the participant's end of study visit: -

- 1. Go to REDCap, using the participant's study ID-
 - Complete the Edinburgh Postnatal Depression Scale (EPDS) e-form for six months visit
 - Complete the Maternal infant bonding scale e-form for six months visit
 - Complete the fatigue Scale e-form for six months visit
 - Complete the quality-of-life scale (WHOQOL BREF) e-forms for six months
 - Evaluate for the presence of any symptom and sign (adverse event(s) AEs)) and if any,
 complete and submit the adverse event e-form.

The visit e-CRF will be available to you ONLY after completing and submitting the above steps on REDCap.

- Complete follow-up visits e-CRF for six months and relevant source documents.
 - **Take blood samples for laboratory tests** as indicated for visit type and complete the blood sample collection log on REDCap.
 - Counsel as appropriate based on any queries they might have about their health or that of their newborn. Counsel and necessary referral (e.g., family planning clinic, psychosocial support etc.)
 - Thank participant for their participation and inform them of plans for dissemination of research findings.

2. Additional steps

• Site coordinators will complete **end of study e-CRF** (Appendix xvi) at completion of all study visits and data entry and other relevant source documents.

4.10.6 Community tracking and home visits for follow up

Postnatal care attendance is very low amongst Nigerian women (NDHS 2018). It can therefore be difficult to retain them within a clinical trial during the postnatal period. To avoid loss to follow up, participants will be followed up to the communities and their homes.

The following steps MUST be taken to avoid loss to follow up and to track those who fail to keep scheduled visits:

- Continuous interaction with participants at every visit to reaffirm comprehension of the nature and purpose of the study, duration of participation, procedures to be done.
- Re-affirm permission to track and for home visit when necessary, including the possibility to collect information and blood samples for laboratory tests during the home visits.
- Reconfirm participant's phone numbers and information on participants locator form at every visit
 and discuss possible physical location of participant for the next scheduled visit and document it
 in the locator form.
- All participants visit schedules must be closely monitored.
- Reminders for next scheduled visit must be sent by test message, WhatsApp, or email as convenient at least 1 week to the scheduled visit.
- A phone call should be made a day prior to scheduled visit.
- Offer to cover transport cost/other compensation for the visit.
- In the event that a participant fails to keep a scheduled appointment, community tracking of the participant must be activated using the participant's locator form and a home visit made within 48 hours.
- Participants will be continuously engaged in the trial by sending text messages about study progress.

The tables below list all the assessments and indicates with an "X" the visits when they are performed. All data obtained from these assessments must be supported in the patient's source documentation and the e-CRFs. The Table also indicates which data are entered into the database (D) or remain in source documents only (S) or both (S, D).

- Assessments that generate data for database entry and which are recorded on CRFs are listed using the CRF name (Enrollment, follow up visits, and end of study).
- Assessments that are transferred to the database electronically (e.g., laboratory data) are listed by test name.

Table 3: Assessment and schedule for study participants

Phase Activity		Baseline	Follow up visits (postpartum)			End of study (EOS)
		(Screen &enroll)				
Study visits no			2 weeks	6weeks	12weeks	6months
Inclusion/exclusion criteria (S,D)		X				
Written informed consent (S)		X				
Socio-demographics/PMH (S,D)		X				
Concomitant medication (S,D)		Х	X	Х	Х	X
Clinical symptoms (S,D)		X	Х	Х	Х	X
Physical examination (S,D)		Х	Х	Х	Х	Х
Lab Tests (S,D)	Hb	Х	Х	Х	Х	X
	Malaria	Х	Х	Х		
	FBC	X	Х	Х		X
	Iron panel	Х		Х		X
	Maternal Serum P04 and other markers	Х	X (Ca, PO4 &	Х		
			ALP only)			
Intervention drug (FCM); S, D		X				
Control drug (FS); S, D		X	X	X		
Adverse Events (S, D)		Х	Х	Х	Х	Х
Edinburgh Postnatal Depression Scale (EPDS) (D)				Х		Х
Mother to infant bonding scale (D)				Х		X
Fatigue scale (D)				X		Х
Quality of life scale (D)				Х		X
Implementation data collection (D)						X
End of study (D)						X

Note: All Participants will be recruited from the postnatal wards from 6 hours after delivery, followed up at home or hospital two weeks later, seen again at six weeks, 12 weeks, and six months postpartum.

^{*} Iron panel comprises serum iron, serum ferritin, transferrin saturation and percentage transferrin saturation. FCM: Ferric carboxymaltose. FS: Ferrous sulphate. S: Source document. D: Database (REDCap e-forms).

5 PARTICIPANTS WITHDRAWAL AND STUDY DISCONTINUATION

5.1 Premature participant withdrawal from the trial

A participant must be withdrawn from the study for any of the following reasons:

- Voluntary withdrawal of informed consent
- Participant could also be withdrawn at any time if the investigator concludes that it would be in the participant's best interest for any reason.

Protocol violations should not lead to patient withdrawal unless they indicate a significant risk to the participant's safety.

Participant may voluntarily withdraw from the study for any reason at any time during the study. If premature withdrawal occurs for any reason, the investigator must determine the primary reason for the premature withdrawal from the study and record this information on the study completion CRF. Participants who are prematurely withdrawn from the study will not be replaced by newly enrolled participants.

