Premature patient withdrawal	Point/time when the patient exits from the study prior to the planned completion of all study drug administration and assessments; at this time study drug administration is discontinued, and no further assessments a planned					
Principal Investigator	The Principal Investigator (PI) is the individual responsible for the conduct of the research at the state level and have coordinating and oversight responsibilities for all study site in their state.					
Site Coordinator (Clinician)	The site coordinator (clinician), SC is the person at each study site responsible for the day to day running of the research project.					
Source Document	A source document is a document in which data collected for a clinical trial is first recorded e.g patient's clinical note/file, registers, logs etc. This data is usually later entered in the case report form.					
Study drug	Any drug (control or investigational) administered to the patient as part of the required study procedures; includes investigational drug and any control drugs					
Study drug discontinuation	Point/time when patient permanently stops taking study drug for any reason; may or may not also be the point/time of premature patient withdrawal					

Study ID	A number assigned to each patient that is enrolled into the study. When combined with the center number, a unique identifier for each patient in the study is created. This is done automatically during the randomization process.
Variable	Information used in the data analysis; derived directly or indirectly from data collected using specified assessments at specified time points

INTRODUCTION

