5.2 Alternate/Further treatment and evaluation

Where any participant fails to respond adequately to study treatment and moderate-severe anemia persists despite iron therapy, such participants will be further evaluated for other forms of anemia and/or referred to specialist hematologist for further evaluation of other causes of anemia at any point during follow up. Relevant information on alternate or additional treatment must completed in the source document and the e-CRF and the participants must be followed up to the end of the study.

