6.5 Study drug discontinuation

- Study drug must be discontinued for a given participant if the investigator determines that continuing it would result in a significant safety risk for that patient. This should only be done after discussion with and approval from the chief investigator/PI.
- The following circumstances require study drug discontinuation:
 - Emergence of severe adverse reactions such as severe nausea/vomiting, allergy, severe pruritus, anaphylaxis, and other life-threatening symptoms
 - Abnormal laboratory values: Hb <6g/dl

Participants who discontinue study drug for adverse effects (AE) or any reason other than an AE will be followed to study completion at 6 months postpartum at which times all the assessments as listed for the visits will be performed. Reasons for study drug discontinuation should be completed, giving the date and primary reason for stopping the study drug under the relevant section of the CRF.

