11 PROTOCOL VIOLATIONS AND DEVIATIONS

11.1 Protocol violations

Any deviation that may affect the subject's rights, safety, or welfare, and/or the completeness, accuracy, and integrity of the study data. This is considered a major, more serious, variance from an approved protocol than a deviation.

Examples of protocol violations

- Omission or inadequate administration of informed consent.
- Inclusion/exclusion errors
- Treatment errors: no treatment or incorrect treatment (including dose or regimen, expired product), participant compliance problems.
- Forcing a participant to enter or remain in the study, failure to withdraw a subject meeting withdrawal criterion.
- Inadvertent loss of samples or data.
- Participants who should have been discontinued from the study due to protocol criteria, but were not
- Working under an expired professional license/certification, debarred or disqualified status

The investigator will notify the Ethics committee in writing as soon as possible and document on the Protocol Deviation/Violation Form (*Appendix* xxv) the reasons for protocol violation and ensuing events. Protocol violations may also be identified by the clinical monitors during the periodic and closeout monitoring visits as well as during in house monitoring.

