 In the rare instance of any moderate/severe AEs such as hypophosphatemia and anaphylaxis, trained research staff will effectively resuscitate and transfer care to higher level health facility for adequate care at no cost to the participant.
- Participants can voluntarily withdraw from the study for any reason at any time and could also be withdrawn at any time if the investigator concludes that it would be in the patient's best interest for any reason.
- All participants will receive folic acid and vitamin C supplementation as normally prescribed.
- The participants will enjoy equal rights and quality care all through the duration of the research.
- Environmental issues are not applicable to this study.

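### Section 5.1 lets an investigator's decision end all outcome collection, and the protocol does not say how this ranks against the follow-up rules in 5.2 and 6.5

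*Protocol*

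**What the plan says.** Five parts of the protocol bear on what happens to outcome data once a woman's treatment or participation changes.

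- **Section 5.1** opens with "A participant must be withdrawn from the study for any of the following reasons". Two items follow. The first is withdrawal of consent. The second reads "Participant could also be withdrawn at any time if the investigator concludes that it would be in the" participant's best interest, whatever the reason. Withdrawn women are not replaced.
- **Section 14.1** repeats the second item: a participant "could also be withdrawn at any time if the investigator concludes that it would be in the patient's best interest for any reason". Neither section says whether outcomes are still collected.
- **The glossary** entry for premature patient withdrawal says "at this time study drug administration is discontinued, and no further assessments a planned". A separate entry defines study drug discontinuation as an event that may or may not coincide with withdrawal.
- **Sections 5.2 and 6.5** preserve follow-up. Of women whose moderate or severe anemia persists, 5.2 says "the participants must be followed up to the end of the study". Of women who stop study drug for an adverse event or any other reason, 6.5 says they "will be followed to study completion at 6 months postpartum at which times all the assessments as listed for the visits will be performed".
- **Section 11.1** lists as violations a failure to withdraw a subject who meets a withdrawal criterion, and also "Participants who should have been discontinued from the study due to protocol criteria, but were not".

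**The concern.** The same woman can fall under two rules with opposite consequences for her data. Under 5.1 and the glossary, assessments end. Under 5.2 or 6.5, they continue to six months. Nothing says which rule prevails.

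The choice is made by people who know the arm and can see how she is doing. The oral arm takes study drug until six weeks while the FCM arm receives one infusion (section 4.6.1), so unequal use of the clause between arms is plausible, though not certain. If its use depends on arm and condition, the missing six-week hemoglobin is informative for the primary endpoint. Later outcomes, such as depression, fatigue and six-month safety, would be lost for the same women.

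Elsewhere the protocol works hard to avoid missing data: a home visit within 48 hours of a missed appointment (4.10.6), and no lost-to-follow-up label until seven months postpartum (5.3). The investigator item in 5.1 bypasses those safeguards.

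**Working it through.** **Step 1: what investigator withdrawal does to the data.** Section 5.1 concerns withdrawal from the study, not from study drug. The glossary ends assessments at that point. The primary outcome is hemoglobin of at least 11.0 g/dl at six weeks (3.1.1). The Primary Analysis set requires the two- and six-week visits, and the intention-to-treat set as defined requires at least one post-baseline efficacy assessment (9.3). A woman withdrawn before six weeks therefore has no primary outcome and leaves the Primary Analysis set. If she has no post-baseline efficacy assessment, she also leaves the intention-to-treat set.

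**Step 2: where the triggers overlap.**

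| Situation | Rule that keeps her | Rule that can remove her |
|---|---|---|
| Significant safety risk | 6.5: drug stopped, all assessments to six months | 5.1: a violation showing significant safety risk may lead to withdrawal; also the best-interest item |
| Poor response | 5.2: followed to end of study | 5.1: best interest, no carve-out |

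The thresholds also differ. Stopping drug under 6.5 needs discussion with, and approval from, the chief or principal investigator. Section 5.1 states no such step for withdrawal from the study.

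**Step 3: mandatory or discretionary.** The 5.1 lead-in says *must*; the investigator item beneath it says *could*. If *must* governs, a woman judged to meet the best-interest item meets a withdrawal criterion, and 11.1 makes keeping her a violation. If *could* governs, there is nothing to violate. The text does not settle this.

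**Step 4: illustration of size.** The protocol gives no rate of investigator-decided withdrawal, so there is no stated figure to reproduce for the concern itself. Inputs from section 4.3: anemia 39% (oral) and 30% (FCM), 700 per arm, 10% loss, final two-sided alpha 0.0492 (critical value 1.967). Evaluable per arm: 700 × 0.90 = 630.

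Power = Φ[(d − 1.967·SE0)/SE1], with SE0 from the pooled proportion and SE1 from the separate proportions.

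- *Plan's rates.* d = 0.090, SE0 = 0.02678, SE1 = 0.02666. (0.090 − 0.0527)/0.02666 = 1.40, so power is about 92%, near the stated 90%. RR = 0.30/0.39 = 0.77.
- *Assumption: 3% of controls (21 of 700) and 1% of the FCM arm (7 of 700) are withdrawn before six weeks, and all would have been anemic.* The observed rate is (p − w)/(1 − w), where w is the share withdrawn. Control: (0.39 − 0.03)/0.97 = 37.1%. FCM: (0.30 − 0.01)/0.99 = 29.3%. d = 0.078, RR = 0.79. SE0 = 0.02653, SE1 = 0.02644. (0.0782 − 0.0522)/0.02644 = 0.98, so power is about 84% with 630 per arm. Removing the withdrawn women from the 630 as well gives about 83%.

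Other assumed shares, all withdrawn women anemic:

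| Control / FCM withdrawn | Observed rates | RR |
|---|---|---|
| 2% / 0% | 37.8% vs 30.0% | 0.79 |
| 5% / 2% | 35.8% vs 28.6% | 0.80 |
| 5% / 0% | 35.8% vs 30.0% | 0.84 |
| 5% / 5% | 35.8% vs 26.3% | 0.74 |
| 1% / 3% | 38.4% vs 27.8% | 0.73 |
| 10% / 10% | 32.2% vs 22.2% | 0.69 |

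Against 0.77 with no loss, the relative risk moves either way. It falls even when the shares are equal, because removing anemic women lowers the smaller rate proportionately more.

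**The case against.** The strongest reply is that 5.1 is a general residual clause and that specific rules already govern the obvious cases. Severe nausea or vomiting is named in 6.5 as a reason to stop study drug, with follow-up continuing. Persistent moderate or severe anemia is covered by 5.2, again with follow-up. This largely stands, and it limits the point in four ways.

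- A reader might infer that six-week hemoglobin is lost for exactly the women doing badly. The documents do not support that: those are the women 5.2 and 6.5 expressly retain. Hemoglobin is also lost only if withdrawal comes before six weeks.
- A reader might infer from 11.1 that keeping a woman in the study is a violation. That holds only if the *must* lead-in governs the *could* item. The clause on failure to withdraw shares a bullet with forcing someone to remain in the study, which suggests withdrawn consent, and both examples can apply to withdrawn consent without conflict.
- A reader might call 5.1 a direct contradiction of 5.2 and 6.5. The glossary treats stopping drug and withdrawal as separate events that may coincide, so this is an unresolved overlap.
- A reader might conclude that the best-interest clause serves no safety purpose because 6.5 already allows drug to be stopped. Participation also involves blood sampling, home visits and tracking, and after a single infusion there is no drug left to stop. The clause can address burdens that 6.5 does not.

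The reply does not supply a precedence rule, and it does not change the glossary's statement that assessments end.

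**Conclusion.** The concern holds as a gap in the wording. An open-label, investigator-decided withdrawal for any reason ends outcome collection, overlapping rules require it to continue, and the protocol does not rank them. The *must*/*could* inconsistency also leaves the reach of the 11.1 violation examples unclear.

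The consequence is possible missingness that depends on arm and condition. Its size and direction are unknown. The shift from RR 0.77 to 0.79 and from about 92% to about 84% power rests on two assumptions absent from the protocol: the 3%/1% split, and every withdrawn woman being anemic, which is the extreme case. It shows that a few women can matter; it does not predict bias. This is a worthwhile, inexpensive improvement. Whether a given woman should be withdrawn or stop treatment is a clinical matter and is not judged here.

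**What to change.** Reconcile 5.1, 14.1, the glossary and 11.1 with 5.2 and 6.5, leaving the investigator's best-interest discretion in place:

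- In 5.1 and 14.1, state that after an investigator decision the scheduled outcome assessments, at minimum the six-week hemoglobin, continue unless the woman withdraws consent to follow-up. Both sections must change together, or a new inconsistency arises.
- In 5.1, resolve *must* against *could*, and say how the section relates to 5.2 and 6.5.
- In the glossary, limit the end of assessments to withdrawal of consent to follow-up.
- In 11.1, distinguish discontinuation of study drug from withdrawal from the study, so that sites know which criteria the violation examples refer to.

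This is a wording amendment that adds no scheduled visits. The cost is some extra follow-up effort for a few women whose files would otherwise have been closed.
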